#### 9.4.3 Handling of Missing Data

At the time of each interim analysis, some subjects will not have completed the full 12-month evaluation period. For example, recently enrolled subjects who are currently failure-free but have only been observed for a portion of the observation period will have "censored" final outcomes. Some subjects may still be within the 13-week blanking period, and have no follow-up time during the observation period. Some subjects may be lost to follow-upA longitudinal model will be employed to enable final observations to be multiply imputed for those subjects with partial or no follow up. Details are included in Appendix B of the protocol version 3.0.

The model is a piecewise exponential model for the time-to-failure during the 39-week post-blanking period. The model has three distinct segments: (0, 2], (2, 8], and (8, 39] weeks. The probability of failure during each interval is exponentially distributed, with different hazard rates in each segment. The model is:

$$f(t) = \exp(-th(t)),$$

where

$$h(t) = \begin{cases} \lambda_1 & 0 < t \le 2; \\ \lambda_2 & 2 < t \le 8; \\ \lambda_3 & 8 < t \le 39. \end{cases}$$

These intervals are based on the model used in the ThermoCool Pivotal trial .

Noninformative Gamma (1, 1) prior distributions will be used for each  $\lambda$  in the model.

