#### 6. LEVEL OF SIGNIFICANCE

The type I error for the interim and final analyses of the primary endpoints is controlled at one-sided 5%.

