#### 8. SAMPLE SIZE JUSTIFICATION

The final analyses for primary safety and effectiveness endpoints will apply Bayesian methods and use a beta-binomial model .

The power calculations for the Bayesian adaptive design are presented in the simulation report Appendix B Table 6 (probability of success). Under the assumption of 65% success rate for primary effectiveness and 8% rate for primary safety, with 330 subjects, assuming 10-15% attrition rate, we will have more than 90% power for declaring success for each of the primary endpoints controlling the type-I error at 5%.

The total of 330 enrolled subjects includes 280 subjects who will be treated using STSF catheter with EPU and 50 subjects be treated using ST catheter with EPU. Approximately 30 subjects may be excluded or discontinued before receiving treatment assuming 10-15% attrition rate.

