#### 9.4 Analysis of Primary Endpoints

The primary effictiveness endpoint is the proportion of patients that are free from primary effectiveness failure at Month 12. The failure modes are defined in the section 5.1.1. The effectiveness success rate at Month 12 will be compared against the performance goal of 50%. The final analyses will apply the Bayesian methods using a beta-binomial model. The analysis population for the primary effectiveness endpoint will be the per protocol (PP) population.

The primary safety endpoint is the proportion of patients that had Primary Adverse Event (PAE) within 7 days (PV stenosis and atrio-esophageal fistula may occur up to 3 months). The PAE rate will be compared against the performance goal of 14%. The final analyses will apply the Bayesian methods using a beta-binomial model. The analysis population for the primary safety endpoint will be the safety population.

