#### 9.4.1 Final Analysis

The primary goal of the trial is to demonstrate effectiveness and safety. For the trial to be successful, both endpoints must be statistically significant relative to their respective PG goals.

The effectiveness endpoint will be assessed by testing the hypotheses:

$$H_0$$
:  $Pr(p > 0.5|x, n) \le 0.97$  vs.  $H_A$ :  $Pr(p > 0.5|x, n) > 0.97$ 

where p is the responder rate, x is the observed number of patients that are failure-free through 12 months ("responders"), and n is the number of subjects in the PP population. If the posterior probability of the primary effectiveness endpoint meeting the 50% PG is greater than 97%, then we meet the threshold for primary effectiveness success.

We model the number of responders

$$X \sim \text{Binomial}(n, p)$$
,

We use a Beta (0.01, 0.01) prior distribution. This prior is centered at 50% and has an effective sample size of 0.02 observations.

Then the posterior distribution is

$$(p|x,n) \sim \text{Beta}(0.01 + x, 0.01 + n - x).$$

Subjects with missing data on the effectiveness endpoint will have their outcomes multiply imputed from a longitudinal model.

Similarly, the hypothesis test for the safety endpoint is:

$$H_0$$
:  $\Pr(q < 0.14|y, n) \le 0.95$  vs.  $H_A$ :  $\Pr(q < 0.14|y, n) > 0.95$ 

where *q* is the PAE rate, y is the observed number of subjects who had PAE and n is the number of subjects in the safety population. If the posterior probability of the primary safety endpoint meeting the 14% PG is greater than 95%, then we meet the threshold for primary safety success.

We model the number of patients with PAE as

$$Y \sim \text{Binomial}(n, q)$$

with Beta(1, 1) prior distribution on q. No imputation for missing data will be performed for the safety endpoint.

The trial will be considered a success if BOTH

- 1. Pr(p > 0.5|x, n) > 0.97 AND
- 2. Pr(q < 0.14|y, n) > 0.95.

These thresholds control the overall Type I error rate for the trial below one-sided 5%. The Type I error for each endpoint individually is also below 5%. The protocol Appendix B contains a detailed description of the statistical methods planned for testing the hypotheses around the primary effectiveness and safety endpoints.

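### The imputation formula printed in SAP 9.4.3 and Protocol 7.9.4.3 is not the piecewise exponential model that the text names; coded literally, it would misstate imputed success, mainly at interim 1

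*SAP*

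**What the plan says.** SAP 9.4.3 and Protocol 7.9.4.3 describe the same model for time to failure over the 39 weeks after blanking. It has segments (0, 2], (2, 8] and (8, 39] weeks and a Gamma(1, 1) prior on each hazard. On the hazards the text says: "The probability of failure during each interval is exponentially distributed, with different hazard rates in each segment". Both documents then print f(t) = exp(−t·h(t)), where h(t) is λ1, λ2 or λ3 according to the segment that contains t.

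The model has two uses. At each interim it completes the outcomes of STSF subjects who have not reached 12 months, and the completed data drive the 99% predictive-probability rule (SAP 9.4.2). At the final analysis it imputes missing effectiveness outcomes (SAP 9.4.1). Details are left to a protocol appendix, called B in the SAP and C in the Protocol, which is not in the text available here. SAP 6 states: "The type I error for the interim and final analyses of the primary endpoints is controlled at one-sided 5" per cent.

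**The concern.** In a piecewise exponential model, survival to t is exp(−∫h), with each segment's hazard acting only over the time spent in that segment. The printed expression multiplies the whole of t by the hazard of the segment that t has reached. A subject projected to week 39 is therefore given λ3 for all 39 weeks, and λ1 and λ2 drop out.

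This is the only formula given for imputing the primary effectiveness outcome. A programmer who followed it would give wrong completion probabilities to subjects with little post-blanking follow-up, who are most numerous at interim 1. The result would enter the early-success decision, which SAP 9.4.2 links to a premarket submission. The sensitivity analyses in SAP 9.4.4 run only after the 12-month visits, so they would not protect an interim declaration.

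**Working it through.** **1. The plan's own figure.** SAP 8 gives its planning inputs: "Under the assumption of 65% success rate for primary effectiveness and 8% rate for primary safety, with 330 subjects, assuming 10-15% attrition rate". On that basis it puts the power above 90% for either primary endpoint, at a type I error of 5%. For effectiveness, "We use a Beta (0.01, 0.01) prior distribution" with a posterior threshold of 0.97 against 50%; for safety, Beta(1, 1) with a threshold of 0.95 against 14%. At a fixed sample size without interims:

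- 15% attrition, n = 330 × 0.85 ≈ 281: effectiveness needs at least 157 responders, power 99.9%; safety allows at most 29 events, power 93.4%.
- 10% attrition, n = 330 × 0.90 = 297: at least 165, power 99.97%; at most 31, power 94.7%.

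The stated power reproduces. It does not test the imputation formula, for which the documents give no numerical result.

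**2. Named model against printed formula.**

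- Named model: S(39) = exp(−2λ1 − 6λ2 − 31λ3).
- Printed: f(39) = exp(−39λ3).
- Ratio, printed to named: exp{2(λ1 − λ3) + 6(λ2 − λ3)}.

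The printed value is too high if the average hazard over the first 8 weeks exceeds λ3, exact if the hazards are equal, and too low if hazards rise. It is not a density either. With one constant hazard and S(39) = 0.65, λ = 0.4308/39 = 0.01105, and ∫exp(−λt)dt over 39 weeks is 0.35/0.01105 ≈ 31.7, when a density cannot integrate to more than 1.

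**3. Assumed hazards.** The documents give none, so I split the cumulative hazard −ln 0.65 = 0.4308 over the segments. For a 20/30/50% split (steeply falling):

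- λ1 = 0.0862/2 = 0.0431, λ2 = 0.1292/6 = 0.0215, λ3 = 0.2154/31 = 0.00695.
- Week 2: the formula jumps from exp(−2λ1) = 0.917 up to exp(−2λ2) = 0.958.
- Week 8: it jumps from exp(−8λ2) = 0.842 up to exp(−8λ3) = 0.946.
- Week 39: exp(−39 × 0.00695) = 0.763, against a true 0.650.

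The printed week-39 value is 0.684 for a 10/20/70% split (mildly falling), 0.650 for constant hazards and 0.621 for a 2/10/88% split (rising, where the jumps are downward).

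**4. Who is affected.** A subject failure-free to t should be imputed a success with probability S(39)/S(t). Past week 8 both forms give exp{−(39 − t)λ3}; at t = 13 both give 0.835. At t = 5 under the steep split the named model gives 0.756 and the printed form exp{−(39λ3 − 5λ2)} = 0.849.

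**5. Interim simulation.** Assumptions: 252 STSF subjects (280 × 0.90), uniform 12-month accrual, 5% loss, Gamma(1, 1) posteriors, 1,000 trials per setting. Here the printed formula is used only to project outcomes, capped at 1. Mean completed success at interim 1:

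| True rate, hazards | Named model | Printed |
|---|---|---|
| 65%, steeply falling | 64.7% | 66.2% |
| 65%, mildly falling | 64.6% | 65.1% |
| 65%, rising | 64.5% | 64.1% |
| 50%, steeply falling | 49.8% | 51.7% |

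Repeat runs put the steep-split shift at 1.4 to 1.5 points at a true 65% and 1.6 to 1.9 at a true 50%. With constant hazards it is about 0. A hand check agrees: about 16% of subjects (0.164 × 252 ≈ 41) have 8 weeks or less of follow-up. Some 88% of these are still failure-free (S(4) = 0.879), so about 36 are overstated by roughly 0.10 each: 36/252 × 0.10 ≈ 1.4 points.

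At a true 50% under the steep split, the effectiveness criterion for early success is met in 0.2% (named) and 0.6% (printed) of trials. At interim 2, about 1% of subjects have 8 weeks or less, the shift is at most 0.12 points, and the early-success rate is unchanged (0.4% and 0.4%).

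**6. If the formula were also the likelihood for the hazards.** All of a subject's time is then credited to the segment where follow-up ended, which inflates exposure in the last segment. At a true 50%, mean completed success at interim 1 is 56.7 to 58.2%, and the effectiveness criterion is met in 16 to 26% of trials (17 to 28% in a repeat run). At interim 2 the mean is 51.3 to 52.6% and the criterion is met in about 1.5 to 1.9% (2.2 to 2.7% in the repeat). The direction is upward under all the patterns, including rising hazards.

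**The case against.** The strongest reply is that this is a slip of notation. The prose names the right model, SAP 9.4.4.4 calls its monthly-segment alternative a more flexible model of the same kind, and the implementation sits in an appendix that cannot be checked here. That stands: nothing shows that the printed form was coded.

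A reader might infer that imputed success is too high at the interims. The documents do not support that. Neither says that hazards fall, and with projection-only use the sign depends on it. The monitoring schedule makes a fall plausible: transmissions go from weekly to monthly after month 5, about (150 − 90)/7 ≈ 8.6 weeks after blanking, close to the week-8 cut. The 12-month Holter pushes the other way. Interim 2 is in any case almost untouched, because nearly everyone is then past week 8.

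A reader might also infer that the type I error claim fails. Under projection-only use the early-success rate at a true 50% stays far below 5%. Only the likelihood reading threatens the claim, and nothing shows that it was used.

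It is also true that an early declaration does not stop follow-up, that full 12-month results are reported, and that the final analysis has complete-case, alternative-imputation and tipping-point checks. These limit the harm at the end of the study. They do not make the printed formula a usable specification.

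**Conclusion.** The formula is wrong as written in both documents and contradicts the model named beside it. That conclusion rests on algebra alone.

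The consequence is conditional. If the formula were coded literally for projection, interim 1 would be misstated by about −0.4 to +1.4 points at a true 65%, and by up to about +1.8 at a true 50%, depending on how the hazards move. Interim 2 would be essentially unaffected. At the final analysis only subjects lost within about 8 weeks after blanking would be affected. If the formula were also used to estimate the hazards, the error at interim 1 would be upward and large enough to matter for early success. The sizes rest on the assumed hazard splits, 252 STSF subjects, uniform accrual and 5% loss. A definite upward bias, or a failure of error control, is not established.

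**What to change.** In SAP 9.4.3 and Protocol 7.9.4.3, replace the formula with

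S(t) = exp{−[λ1·min(t, 2) + λ2·min(max(t − 2, 0), 6) + λ3·max(t − 8, 0)]},

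label it as the probability of remaining failure-free to week t after blanking, and state that a subject failure-free to t is imputed a success with probability S(39)/S(t). Give the appendix one name in both documents.

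Confirm that the appendix simulations and the analysis code used this form, both for estimating the hazards and for projecting outcomes. If they did, the cost is one line per document and a code check. If they did not, the operating characteristics must be rerun and the type I error and power statements checked against the new results. Nothing else in the design changes.

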#### 9.4.4 Sensitivity Analyses

To investigate the robustness of primary analysis result of primary endpoints, several sensitivity analyses will be performed. These sensitivity analyses will be performed after all of the subjects complete or reach the 12 months visit and results will be presented in the final CSR.

#### 9.4.4.1 Snap-Shot Binomial Analysis of Primary Endpoints

In the PP population, exact binomial analysis will be performed to assess the primary effectiveness outcome. In the safety population, exact binomial analysis will be performed to assess the primary safety outcome. The subjects with missing outcomes will be excluded from the analysis.

#### 9.4.4.2 KM Curve Analysis

Kaplan-Meier estimate will be used to characterize the time to first AF/AT/AFL recurrence following initial ablation procedures in the PP population. The survival probabilities of AF/AT/AFL recurrence at each of the monthly follow-up time point post blanking along with the corresponding 90% confidence intervals using Greenwood's formula will also be presented. This analysis would be descriptive.

#### 9.4.4.3 Full Set Effectiveness Population

Some subjects in the clinical studies may be enrolled and treated with the study cathether using EPU, however, may be later found not to meet the inclusion and exclusion criteria due to missing documentation or other reasons. In order to assess the effectiveness outcomes of these subjects as well, the exact binomial analysis and the KM analysis will be repeated in the Full Set Effectiveness Population.

#### 9.4.4.4 Alternative Exponential Model for Imputation

In the final Bayesian analysis, a more flexible piecewise exponential model with one segment for each month will also be applied to impute the missing outcomes for the primary effectiveness endpoint.

#### 9.4.4.5 Multiple Imputations of Missing Data in PP Population

Multiple imputation  will be used to impute missing data for the effectiveness outcome in the PP population. 5 imputed datasets will be generated (M=5). The MI procedure in sas studio (PROC MI and PROC MIANALYZE) will be used to perform these analyses.

#### 9.4.4.6 Tipping Point Analysis of Missing Data

Tipping point analysis  will be performed in the PP population to assess the impact of missing effectiveness outcomes. Tipping point analysis will also be performed in the safety population to assess the impact of missing safety outcomes if there is any.

#### 9.4.5 Subgroup Analyses

For the primary endpoints, subgroup analysis will be performed for the following subgroups after the 12 months follow-up is complete.

PP population will be used for primary effectiveness endpoint and safety population will be used for primary safety endpoint. The number and percentage of subjects with the primary effectiveness and safety endpoints will be presented in each subgroup. Exact 95% confidence intervals will be constructed around the percentages in each subgroup. Fisher's exact test will be used to test for statistical difference between the subgroups at the 5% significance level. Fisher-Freeman-Halton Exact Test will be used when the number of subgroup is greater than two. Since subgroup analyses are unadjusted, any differences especially in subgroups defined based on post-baseline characteristics, may be confounded by differences in baseline characteristics. For e.g., repeat procedure vs. no repeat procedure during the blanking period – patients with more advanced disease at baseline may require a repeat procedure impacting the observed safety and effectiveness rates.

- Age group: <60 vs. >=60 years
- Previously failed AAD Class I&III vs Class II&IV
- Repeat procedure during blanking period: Repeat procedure conducted vs. Not conducted
- Operator's ablation procedure experience level: More experienced (≥ 75 left atrial ablation procedures for atrial fibrillation in the past 12 months) vs. Less experienced (< 75 left atrial ablation procedures for atrial fibrillation in the past 12 months)
- Segments of Tag Index values: above or below or at target Biosense Webster, Inc

- Contact Force: <=10, 11-15, 16-20 and >20 grams
- Ablation targets

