#### 1. STUDY DESIGN

The SURPOINT COA study is a prospective, multicenter, non-randomized clinical evaluation of the VISITAG SURPOINT Module with EPU when used with the THERMOCOOL SMARTTOUCH® SF catheter (STSF) catheters or the THERMOCOOL SMARTTOUCH® (ST) catheter in treating subjects with symptomatic paroxysmal atrial fibrillation (PAF) who have failed at least one antiarrhythmia drug. A maximum of 330 subjects will be enrolled across up to 45 sites. Two hundred eighty (280) subjects will be treated using the STSF catheter with EPU and 50 subjects will be treated using the ST catheter with EPU. A few sites will be selected to enroll subjects to be treated only with the ST catheter. The remaining sites will enroll subjects to be treated with the STSF catheter. Two interim analyses are planned to take place after all subjects who are treated using the STSF catheter with EPU have completed their 3-month and 6-month follow-up visits for the evaluation of early success. The planned interim analysis will be based on data collected only in the subjects who are treated using STSF catheter with EPU. The final analysis of the primary effectiveness and safety endpoints will be based on all subjects's full 12-month follow-up data. Effectiveness and safety endpoints defined in association with the primary study objectives will be compared to the predetermined performance goals.

Enrolled subjects who satisfy all eligibility criteria will undergo the ablation procedure with the catheters and VISITAG SURPOINT Module. After the study ablation procedure, subjects will enter a 3-Month blanking period (Day 0-90). After the blanking period, subjects will enter the evaluation period (Days 91-365). Subjects having AF recurrence and/or receiving therapeutic interventions during the evaluation period will be considered effectiveness failures.

All subjects will undergo follow up visits at defined intervals (refer to Table 5-1 Schedule of Treatments and Evaluations in protocol). Subjects complete the SURPOINT COA study after the 12-month follow up visit.

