#### 9.4.6 Additional Analysis for Primary Effectiveness Endpoint

Univariate and multivariate logistic regression models will be used to examine the impact of the covariates on the primary effectiveness endpoint. If the sites are not poolable, then study site and operators will be treated as random effects in the regression model. All covariates included in the analysis will consist of the following:

	Definition/ Variables	Note
Demographics	
 
Age
 
Gender
 
Ethnicity
 
Race
 
Study Site
 
	
 
Continuous variable (unit: year)
 
Male, Female
 
Hispanic/ Latino or not
 
Asian, Black, Caucasian, Other
 
Random Effect if sites not poolable
 

Medical History	
 
Diabetes
 
Hypertension
 
Structural heart disease
 
Atrial Flutter
 
Duration of AF history
 
Frequency of AF episodes
 
	
Cardiac Medical History	
 
Previously tried Class I AADs
 
Previously tried Class II AADs
 
Previously tried Class III AADs
 
Previously tried Class IV AADs
 
	
 
Class I: Disopyramide, Flecainide, Propafenone, Quinidine
 
Class II: (Beta-Blocker): Acebutolol, Atenolol, Metoprolol, Propranolol, Sotalol, and other Beta-Blocker
 
Class III: Amiodarone, Dofetilide
 
Class IV: Verapamil, Diltiazem
 

TTE Result	Baseline left atrial dimension	
Ablation Procedure	
 
Repeated ablation procedure or not
 
Procedure success
 
Use of Isoproterenol
 
Use of Adenosine
 
Agilis Sheath
 
Other Sheath
 
Total procedure time
 
CF values
 
Average power
 
Average impedance
 
Average temperature
 
Total RF ablation time
 
Tag index value
 
Etc.
 
	

The primary effectiveness endpoint will be the dependent variables and the covariates will be treated as independent variables. Univariate logistic regression models will be conducted for each of the potential predictors. A p-value <0.20 is to be used as the cut-off point for screening covariates. Forward model selection will be used to select predictors that remain significant at p-

value <0.05 in the multivariate model. Interaction terms may be examined based on those covariates that remain significant in the final model.

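### The operator-experience subgroup test (SAP 9.4.5) treats subjects as independent although all patients of an operator share one experience level, so its nominal 5% holds only if operators and sites vary little

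*SAP*

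**What the plan says.** SAP 9.4.5 lists among its subgroups "Operator's ablation procedure experience level: More experienced", meaning 75 or more, against fewer than 75, "left atrial ablation procedures for atrial fibrillation in the past 12 months". The unit counted is the subject: "The number and percentage of subjects with the primary effectiveness and safety endpoints will be presented in each subgroup". Exact 95% intervals are put around each percentage, and "Fisher's exact test will be used to test for statistical difference between the subgroups at the 5% significance level".

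The section carries one caution: "Since subgroup analyses are unadjusted, any differences especially in subgroups defined based on post-baseline characteristics, may be confounded by differences in baseline characteristics". That concerns confounding. It does not mention that subjects share operators or sites.

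Clustering is dealt with in two other places, each time only if the sites fail a poolability test at p<0.15:
- SAP 9.4.5.2 gives a DerSimonian-Laird random-effects estimate of the overall effectiveness and safety rates.
- SAP 9.4.6, which models effectiveness only, says "If the sites are not poolable, then study site and operators will be treated as random effects in the regression model".

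**The concern.** Fisher's test and the exact intervals assume that each subject is an independent observation. For a factor fixed at operator level, the comparison is really between groups of operators. If success or adverse-event rates differ among operators or sites for reasons other than experience, those differences do not average out over some 300 subjects. They average out only over the operators or sites in each subgroup. The test then understates the variance, the intervals are too narrow, and an experience effect is declared too often.

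The stated caution does not cover this, because confounding biases the estimate while clustering affects its precision. The two conditional provisions do not reach the test either: Fisher's test stays unchanged even after the plan has found the sites not poolable. For the safety endpoint, no clustered comparison by experience exists anywhere in the plan.

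At stake is whether a significant experience difference in the final report can be taken at its nominal level.

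**Working it through.** **Inputs from the documents.** "A maximum of 330 subjects will be enrolled across up to 45 sites" (SAP 1). "Approximately 30 subjects may be excluded or discontinued before receiving treatment assuming 10-15% attrition rate" (SAP 8), so about 330 - 30 = 300 treated subjects, or 300/45 = 6.67 per site. Assumed rates are 65% effectiveness success and 8% primary adverse events (SAP 8). No site may exceed about 15% of enrolment, and a site may have several operators (Protocol 5).

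**Inputs that are assumed.** ICC, number of operators per site, share of experienced operators, spread of site sizes, and a two-sided test (sidedness is not stated).

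**Step 1, the plan's own figure.** SAP 8 states more than 90% power for each primary endpoint. I applied the final rule of SAP 9.4.1 (posterior above 0.97 with a Beta(0.01, 0.01) prior for effectiveness; above 0.95 with a Beta(1, 1) prior for safety) with exact binomial sums at n = 300 and without interim looks. Power is 99.97% for effectiveness and 94.0% for safety. At n = 280 it is 99.9% and 93.7%. The statement is reproduced. The documents give no error rate for the experience test beyond its nominal 5%.

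**Step 2, what an ICC means.** The SD of true site success rates is sqrt(ICC × 0.65 × 0.35): 4.8, 6.7, 10.7 and 15.1 percentage points at ICC 0.01, 0.02, 0.05 and 0.10.

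**Step 3, rough check by formula.** With equal sites, the design effect is 1 + (6.67 - 1) × ICC, and the true size of a nominal 5% z-test is 2 × [1 - Φ(1.96/√(design effect))].

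| ICC | Design effect | True size |
|---|---|---|
| 0.01 | 1.057 | 5.7% |
| 0.02 | 1.113 | 6.3% |
| 0.05 | 1.284 | 8.4% |
| 0.10 | 1.567 | 11.7% |

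**Step 4, simulation of Fisher's test with no experience effect.** Settings: 300 subjects, beta-distributed site rates, equal or uneven sites (capped at 15%), 25% or 50% of sites less experienced, 10,000 runs per cell. With independent subjects, rejection is 3.5-4.4% (effectiveness) and 3.0-4.0% (safety), so the test is slightly conservative without clustering. With clustering:

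| Setting | ICC 0.01 | ICC 0.02 | ICC 0.05 | ICC 0.10 |
|---|---|---|---|---|
| Effectiveness, 45 sites | 4.9-5.7% | 5.8-6.2% | 7.2-9.5% | 10-15% |
| Effectiveness, 30 sites | not shown | 5.4-7.4% | 8.9-12.2% | 14-20% |
| Effectiveness, 20 uneven sites | not shown | 8.1-8.6% | 14-15% | not shown |
| Safety, 45 sites | not shown | 4.9-5.7% | 6.1-9.4% | 9-14% |
| Effectiveness, 45 uneven sites, two operators per site, experience set per operator | not run | 5.2-5.3% | 6.8-6.9% | 9.4-10.0% |

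A further set of 3,000 runs per cell (45 uneven sites, half experienced, effectiveness) gave 7.6%, 10.7% and 15.7% at ICC 0.02, 0.05 and 0.10. This is the source of the upper end of about 16%.

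**Step 5, does the remedy work?** Permuting the experience label over whole sites gave about 4-6% rejection in every setting run (both endpoints, ICC 0.02-0.10, 30 or 45 sites). Fisher's test in the same runs gave 4-20%. Permutation over operators within sites was not simulated.

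**The case against.** The strongest reply is that the size is assumed, not found. The documents give no ICC, and an ICC of 0.05 already means that true site rates have an SD of 10.7 points, which is not modest. Protocol 5 expects several operators at a site. If their experience differs, site effects partly cancel, and the inflation at ICC 0.05 falls to about 7%. The comparison is also supportive, unadjusted by its own description, and run after follow-up. All of this stands and limits the size. It does not supply an adjustment that the plan lacks.

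A reader might go further in three directions that the documents do not support:
- **That the test is known to reject at some fixed rate such as 7-14%.** That needs particular assumed ICCs together with experience set by site, and in places fewer than 45 sites.
- **That SAP 9.4.6 must always carry a site or operator random intercept.** When the poolability test is not significant, a site-level covariate is rejected about 6-7% of the time against 5%, at assumed ICCs of 0.03-0.05. Study site is itself a listed covariate, and the regression is exploratory with screening and forward selection. That is too little to require a change.
- **That a false finding would steer operator training.** No section says so. Protocol 5.17.3 bases training on a physician training plan and retrospective cases.

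**Conclusion.** The structural point holds. The operator-experience comparison uses subjects as independent units for a factor shared within operators, and no section corrects the test or its intervals.

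Its size is conditional. At 45 sites and assumed ICCs of 0.01-0.10, a nominal 5% test rejects about 5-16% of the time if experience varies by site. With two operators per site the figure is about 5-10% (run for ICC 0.02-0.10). It is higher with fewer sites. At ICC 0.02 or below with 45 sites the inflation is small to negligible: mostly 5-6%, with 7.6% in the highest single run.

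The importance is minor to moderate. A reader might infer that the trial's conclusion is at risk, but success in SAP 9.4.1 rests only on the two posterior probabilities, and this test enters neither. The assumptions that matter most are the ICC, how experience is distributed within sites, and the number of sites that actually enrol.

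**What to change.** In SAP 9.4.5, for the operator-experience subgroup only:
- Replace Fisher's exact test with a permutation test that reassigns the experience label over whole operators, or over whole sites where operators cannot be separated. Apply it to both primary endpoints, whatever the poolability result.
- Report 95% intervals that allow for clustering by operator or site, in place of the exact binomial intervals.
- State the date at which the 12-month procedure count is taken, so that each operator carries one label. Enrolment itself runs about 12 months (Protocol 9.1), and no reference date is given.

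Permutation is safer here than a logistic model with operator nested in site. At 8% of 300 subjects there are about 24 safety events, or 24/45 = 0.5 per site, which is too few to fit such a model reliably.

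The cost is a short SAP edit and simple code, plus operator identity for each procedure. The comparison will have wider intervals and less power. No change to SAP 9.4.6 or to the primary analysis is needed.
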